14.3.1.2 Unsolicited Adverse Events

Table 39:Summary of Unsolicited Adverse Events by MedDRA System Organ Class and Preferred Term, Dose Number, and Treatment
Group – HEV-239

MedDRA	MedDRA		D Pos	Day 1-8 st Dose (N=X)	8 e 1		D Po	ay 9-29 st Dose (N=X)	9ª e 1		Da Pos	y 29 ^b -: st Dose (N=X)	36 e 2		Da Pos	ay 37-5 st Dose (N=X)	57 e 2		Day Po	y 180- st Dos (N=X)	187 e 3		Day Pos	y 188-2 st Dose N=X)	08 3		Day Pos	y 209-3 st Dose (N=X)	860 e 3]	An Post (y Tim Any E (N=X)	e ^c)ose
Organ Class	Preferred Term	n	%	95% CI	Even ts	n	%	95% CI	Even ts	n	%	95% CI	Even ts	n	%	95% CI	Even ts	n	%	95% CI	Even ts	n	%	95% CI	Even ts	n	%	95% CI	Even ts	n	%	95% CI	Even ts
Any SOC	Any PT	x	xx	xx, xx	x	x	xx	xx, xx	x	x	xx	xx, xx	x	x	xx	xx, xx	x	x	xx	xx, xx	x	x	xx	xx, xx	x	x	xx	xx, xx	x	x	xx	xx, xx	x
[SOC 1]	Any PT																																
	[PT 1]																																
	[PT 2]																																
[SOC 2]	Any PT																																
	[PT 1]																																
	[PT 2]																																

Note: N = number of subjects in the Safety Population. This table presents number and percentage of subjects. A subject is only counted once per PT/time point.

a Day 29 prior to receiving Dose 2

b Day 29 after receiving Dose 2

c Includes all AEs collected Day 1 to Day 57 and Day 180 to Day 360 and SAEs collected from Day 57 to Day 180

Tables with similar format:

Table 40:Summary of Unsolicited Adverse Events by MedDRA System Organ Class and Preferred Term, Dose Number, and Treatment
Group – Placebo

					HEV (N =	7-239 = X)					Pla (N :	cebo = X)					All Su (N =	ıbjects = X)		
ModDDA System	Droforrod		Rel	ated	Not R	elated	To	otal	Rel	ated	Not R	elated	To	tal	Rel	ated	Not R	elated	To	otal
Organ Class	Term	Severity	n	%	n	%	n	%	n	%	n	%	n	%	n	%	n	%	n	%
Any SOC	Any PT	Any Severity	х	XX	х	XX	х	XX	х	XX	х	XX	х	XX	x	xx	х	xx	х	xx
		Mild	х	xx	х	xx	х	xx	х	xx	х	xx	х	xx	х	xx	х	xx	х	XX
		Moderate	х	xx	х	xx	х	xx	х	xx	х	xx	х	xx	х	xx	х	xx	х	XX
		Severe	х	xx	х	xx	х	xx	х	xx	х	xx	х	xx	х	xx	х	xx	х	XX
SOC 1	PT 1	Any Severity	х	xx	х	xx	х	xx	х	xx	х	xx	х	xx	х	xx	х	xx	х	XX
		Mild	х	XX	х	xx	х	xx	х	xx	х	xx	х	xx	х	XX	х	XX	х	xx
		Moderate	х	XX	х	xx	х	xx	х	xx	х	xx	х	xx	х	XX	х	XX	х	xx
		Severe	х	XX	х	xx	х	xx	х	xx	х	xx	х	xx	х	XX	х	XX	х	xx
	PT 2	Any Severity	х	xx	х	xx	х	xx	х	xx	х	xx	х	xx	х	XX	х	XX	х	xx
		Mild	х	xx	х	xx	х	XX	х	xx	х	XX	х	xx	х	XX	х	XX	х	xx
		Moderate	х	xx	х	xx	х	XX	х	xx	х	xx	х	xx	х	xx	х	xx	х	xx
		Severe	x	xx	x	xx	х	xx	x	xx	x	xx	х	xx	х	xx	х	xx	x	xx

Table 41:Unsolicited Adverse Events by MedDRA System Organ Class and Preferred Term, Maximum Severity, Relationship, and
Treatment Group

Note: N = Number of subjects in the Safety Population.

Related Unsolicited Adverse Events Post Dosing by MedDRA System Organ Class and Preferred Term, Dose, and Treatment Table 42: Group – HEV-239

]	Day 1 Post Do (N=Y	-8 ose 1 K)	I	Day 9-2 Post Dos (N=X	29ª se 1)	l F	Day 29 ^b Post Dos (N=X	-36 se 2)	I	Day 37- Post Dos (N=X	-57 se 2)	D F	ay 180- ost Dos (N=X	-187 se 3)	I	Day 188 Post Do (N=2	8-208 ose 3 X)	D I	ay 209 Post Do (N=X	9-360 ose 3 K)
MedDRA System Organ Class	MedDRA Preferred Term	n	%	Events	n	%	Events	n	%	Events	n	%	Events	n	%	Events	n	%	Events	n	%	Events
Any SOC	Any PT	х	xx	х	х	xx	х	х	xx	х	х	xx	х	х	xx	х	х	xx	х	х	xx	х
[SOC 1]	Any PT																					
	[PT 1]																					
	[PT 2]																					
[SOC 2]	Any PT																					
	[PT 1]																					
	[PT 2]																					

Note: N = Number of subjects in the Safety Population. This table presents number and percentage of subjects. For each time point, a subject is only counted once per PT.

a Day 29 prior to receiving Dose 2 b Day 29 after receiving Dose 2

Tables with similar format:

Table 43: Related Unsolicited Adverse Events Post Dosing by MedDRA System Organ Class and Preferred Term, Dose, and Treatment **Group - Placebo**

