6.3.1.13 Visit 14, Day 194 (Day 15 after Second Boost; +/- 2 Days); Clinic Visit

- Obtain vital signs (HR, BP, and oral temperature)
- Perform symptom-directed PE (if needed)
- Evaluate vaccination site (if needed)
- Interview the subject and review the e-Memory aid data. Address any incomplete, missing, or inconsistent data.
- Review of Unsolicited AEs and SAEs.
- Counsel subjects to use adequate birth control methods to avoid pregnancy
- Review concomitant medications.
- Obtain blood for safety laboratories (if needed due to abnormalities at prior visit, Section 2.3.1).
- Obtain serum for immunogenicity assays
- Collect PBMCs and plasma for future assays.

6.3.1.14 Visit 15, Day 208 (Day 29 after Second Boost; +/- 2 Days); Clinic Visit

- Perform symptom-directed PE (if needed)
- Review of Unsolicited AEs and SAEs.
- Counsel subjects to use adequate birth control methods to avoid pregnancy
- Review concomitant medications.
- Obtain serum for immunogenicity assays
- Collect PBMCs and plasma for future assays.

DMID/NIAID/NIH

CONFIDENTIAL

DMID eCTD Compliant Interventional Protocol Template and Instructions, Version 4.0, Dated May 15, 2018

6.3.1.15 Visit 16, Day 270 (Day 90 after Second Boost; +/- 14 Days); Telephone Call

- Review of SAEs.
- Review concomitant medications if associated with an SAE.

6.3.2 Final Study Visit: Visit 17, Day 360 +/- 28 days (Day 180 after Second Boost); Clinic Visit

- Perform symptom-directed PE (if needed)
- Review of SAEs.
- Review concomitant medications if associated with an SAE.
- Obtain serum for immunogenicity assays
- Collect PBMCs and plasma for future assays.

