- 4. Unsolicited Adverse Events (see Section 8.1.3) non-serious adverse events occurring from the time of the first study vaccination until Day 57 and then from Day 180 through Day 208. Unsolicited AEs will be collected at all visits from the time of the first study vaccination until D57, then from Day 180 through 208. Any safety-related changes that occur post-vaccination during these timeframes and that represent an increase in grade must be recorded on the eCRF. Thereafter, recording will be limited to SAEs.

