9.3.2. Unsolicited Adverse Events

The proportion of subjects reporting at least one unsolicited adverse event will be summarized by MedDRA system organ class and preferred term for each vaccination and over all vaccinations. Denominators for percentages are the number of subjects who received the vaccination being summarized.

Adverse events by subject will be presented in Listing 10.

The following summaries for unsolicited adverse events will be presented by MedDRA system organ class, preferred term, vaccination and treatment group:

- Summary of adverse events occurring in 5% of subjects (Table 26);
- Subject incidence and total frequency of adverse events over time with 95% CI (Day 1-8, Day 9-29 (pre-vaccination), Day 29 (post-vaccination)-36, Day 37-57, Day 180-187, Day 188-208, Day 209-360, and anytime post-any dose) (Table 39 and Table 40);
- Summary of severity and relationship to study product (Table 41);
- Subject incidence and total frequency of related adverse events over time (Day 1-8, Day 9-29(pre-vaccination), Day 29 (post-vaccination)-36, Day 37-57, Day 180-187, Day 188-208, Day 209-360, and anytime post-any dose) (Table 42 and Table 43);
- Subject listing of non-serious adverse events of moderate or greater severity (Table 45);

- Bar chart of the frequency of serious and non-serious related adverse events by severity and MedDRA system organ class (Figure 19);
- Bar chart of the incidence of serious and non-serious related adverse events by maximum severity and MedDRA system organ class (Figure 20);

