k) When the memory aid is distributed to subjects, they will also be instructed as to when to contact the investigator about unsolicited AEs. Hypersensitivity symptoms will also be reviewed with the subject and they will be counselled that if any of these were occur they must contact study personnel or seek medical attention immediately.

1) Concomitant therapies between D57 and D150 and from D208 – D360 should only be recorded if administered in conjunction with SAEs.

m) Solicited AEs: Inclusive of solicited injection site reactions and systemic reactogenicity events performed on the day of each study vaccination through at least D8 after each study vaccination (see Protocol Sections 8.1.2). Unsolicited AEs: Collection of unsolicited AEs from time of first vaccination through D57; then from Day 180 – 208. SAEs: SAEs will be collected from the time of the first study vaccination through the last study visit (Day 360).

n) Volumes are the maximum volumes expected to be drawn. Samples may be fasted or non-fasted. The total volume at an unscheduled or early termination visit will not exceed the individual time point volume.

 $\{\ \}$ If indicated based upon timing and/or symptoms.

* See Protocol Section 7.1.1 regarding details of medical history to be collected.

** Telephone Visit

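### The unsolicited-AE tables give Day 209-360 a rate and an interval, and footnote c calls Day 180-360 an all-AE period, although non-serious AEs are not routinely collected after D29 post-Dose 3 (nominal Day 208)

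*SAP*

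**What the plan says.** **Collection.** SAP 4.5.1 states: "Unsolicited AEs will be collected at all visits from the time of the first study vaccination until D57, then from Day 180 through 208". It then adds: "Thereafter, recording will be limited to SAEs". Protocol 8.2 has the same rule, and 8.3, 8.4 and Appendix A footnote m give the same end dates. SAP Table 1 footnote m agrees ("Collection of unsolicited AEs from time of first vaccination through D57", then Days 180 to 208). The visit procedures match. Visit 15 (Day 208, Protocol 6.3.1.14) reviews unsolicited AEs and SAEs, while Visits 16 and 17 (Days 270 and 360, Protocol 6.3.1.15 and 6.3.2) review SAEs only. Unscheduled visits review unsolicited AEs only within Day 29 of a vaccination (Protocol 6.4).

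Protocol 3.1 states the window relative to dose, through D29 after each vaccination. The primary endpoint for vaccine-related unsolicited AEs uses the same window (Protocol 3.3.1, SAP 3.2.1).

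**Reporting.** SAP 9.3.2 plans "Subject incidence and total frequency of adverse events over time with 95% CI" for a list of periods that ends "Day 180-187, Day 188-208, Day 209-360, and anytime post-any dose". The Table 39 shell prints Day 209-360 with n, %, 95% CI and events, and Table 40 copies it. Tables 42 and 43 (related events) carry the same period without a CI. Footnote c to Table 39, attached to the 'Any Time Post Any Dose' column, says: "Includes all AEs collected Day 1 to Day 57 and Day 180 to Day 360 and SAEs collected from Day 57 to Day 180".

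**The concern.** The Day 209-360 column has the same title, layout and interval as columns in which all AEs were collected, and nothing marks it as different. Footnote c reinforces this: it flags the gap before Dose 3 as SAE-only but places the period after Day 208 under full AE collection.

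Safety is a primary objective. Someone reading across Table 39 could see unsolicited AEs fall to few or none after Day 208 and take that as a finding about late tolerability, when part or all of the fall comes from the collection rule. The interval adds to this, because it presents the subjects as having been observed for events that were not asked about.

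**Working it through.** **1. The plan's own figure.** Protocol Table 7 and SAP Table 2 give the chance of seeing at least one event in 20 vaccinees, 1 - (1 - p)^20. For p = 0.01%, 0.1%, 1%, 10% and 20% this gives 0.20, 1.98, 18.21, 87.84 and 98.85%, as printed. These figures are not in dispute.

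**2. Windows side by side (nominal days).**

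| Days | Non-serious AEs | SAEs | Column in Table 39 | Footnote c |
|---|---|---|---|---|
| 1-57 | collected | collected | yes | all AEs |
| 58-179 | not collected | collected | none | SAEs only |
| 180-208 | collected | collected | yes | all AEs |
| 209-360 | not collected | collected | yes, with CI | all AEs |

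The last row is the mismatch. Its length is 360 - 209 + 1 = 152 days, and 152/360 = 42%. The gap before Dose 3 is 179 - 58 + 1 = 122 days.

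**3. What the column prints with no recorded event.** The exact (Clopper-Pearson) upper limit at zero events is 1 - 0.025^(1/n). For n = 20 it is 16.8%, and for n = 5 it is 52.2%. If only 19 or 18 vaccinees receive Dose 3, it is 17.6% or 18.5%.

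**4. How much could go unseen.** The documents give no rate of non-serious AEs for this period, so the rates below are assumptions. The 12% is the Phase III unsolicited-AE rate in Protocol 2.3.1, borrowed for scale only. Expected subjects = 20p; chance of at least one = 1 - (1 - p)^20.

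| Assumed true share | Expected of 20 | Chance of at least one |
|---|---|---|
| 5% | 1.0 | 64% |
| 12% | 2.4 | 92% |
| 20% | 4.0 | 99% |
| 30% | 6.0 | above 99.9% |

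If all 20 are dosed on schedule, routine collection would capture none of these events.

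**5. How often SAEs alone would leave the column at zero.** This is (1 - p)^20. At assumed SAE rates of 0.4%, 1% and 2.5%, it is 92%, 82% and 60%. The 0.4% and 2.5% are Phase III SAE rates in Protocol 2.3.1, measured over different follow-up periods.

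**6. Effect of the Dose 3 window.** Dose 3 may be given at Day 180 +/- 14 (Protocol 6.3.1.10). With the dosing day counted as Day 1, D29 is the dosing day plus 28.

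- On schedule: 180 + 28 = Day 208.
- Latest: 194 + 28 = Day 222, or Day 224 with the +2-day visit window.
- Earliest: 166 + 28 = Day 194.

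The SAP does not say whether the period columns use nominal or actual study day. On actual days, a late-dosed subject's in-window non-serious AEs can fall in Day 209-360, and Days 180-193 precede that subject's Dose 3. An early-dosed subject's AEs on Days 166-179 fall in no period column.

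**The case against.** The strongest defence is that this is a labelling slip with a legitimate column behind it. SAEs are collected to Day 360 and do enter the unsolicited displays (Listing 10 has an SAE field, and Figures 19 and 20 include serious events), so a late column has something to report. The collection window is stated correctly in SAP 4.5.1 and Table 1. SAEs are also shown separately in Tables 25, 26 and 44. The study tests no hypotheses.

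Much of this stands, and it limits what can be claimed:

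- A reader might infer that the column can hold only SAEs and must show a false absence. The documents do not support that. A late SAE would appear, and step 6 shows that in-window non-serious AEs can fall there on actual study days.
- A reader might infer that footnote c vouches for the Day 209-360 column. It marks only the 'Any Time' column. Its error is to misdescribe what that total covers.
- A reader might take 42% as the size of a bias. It is a share of calendar time and nothing more.
- A blanket SAE-only label on Days 209-360 and 58-179 looks like the obvious remedy. On calendar days it would be wrong for subjects given Dose 3 late or early.

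The defence does not remove the mismatch itself. No passage extends routine non-serious AE collection beyond D29 after Dose 3. The AE/SAE assessment marks at Visits 16 and 17 in the schedule are restricted by footnote m. Stating the window elsewhere does not label the table.

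**Conclusion.** The point holds as an error in the planned displays. Followed as written, Tables 39 and 40 would attach a rate and an exact interval to a period in which non-serious AEs were not routinely collected, Tables 42 and 43 would show the same period unlabelled, and footnote c would misstate what the 'Any Time' total covers. Low or zero late rates would partly reflect non-collection.

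The 0/20 (0 to 16.8%) and 0/5 (0 to 52.2%) results assume that every randomised subject receives Dose 3, that no SAE occurs after Day 208, and that no in-window AE of a late-dosed subject is assigned to the column. The number of non-serious events missed cannot be known from the documents; step 4 gives only a range under assumed rates.

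A reader might infer that the trial's main safety result is compromised. It is not. The primary unsolicited-AE endpoint stops at Day 29 after each dose, inside the collection window, and no sample size, analysis population or halting rule changes. The change should be made before the tables are produced.

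**What to change.** 1. In SAP 9.3.2 and Tables 39, 40, 42 and 43, define the period columns by days since the most recent dose, for example Day 1-8, Day 9-29 and after Day 29 post-dose, with the second Dose 1 period closing at Dose 2 as it does now. State this rule explicitly so that AEs of subjects given Dose 3 early or late are placed correctly.
2. In the same four tables, label the period after D29 post-Dose 3: *SAEs only; non-serious AEs not collected*.
3. Replace footnote c with: *all AEs through D29 after each dose (nominal Days 1-57 and 180-208); SAEs only at other times through Day 360*.
4. Optionally, add a separate SAE-only column for the gap before Dose 3.

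The cost is edits to four table shells, one footnote and one derivation rule. Dose dates are already recorded, so no new data are needed.

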14.3.2 Listing of Deaths, Other Serious and Significant Adverse Events

Table 44:Listing of Serious Adverse Events

Adverse Event	Associated with Dose No.	No. of Days Post Associated Dose (Duration)	No. of Days Post Dose the Event Became Serious	Reason Reported as an SAE	Severity	Relationship to Study Treatment	If Not Related, Alternative Etiology	Action Taken with Study Treatment	Subject Discontinued Due to AE	Outcome	MedDRA System Organ Class	MedDRA Preferred Term
Subject II	D: , Treatmen	t Group: , AE Nun	nber:									
Comments	s:											
Subject II	D: , Treatmen	t Group: , AE Num	nber:									
Comments	s:											

Table 45: Listing of Non-Serious, Unsolicited, Moderate or Severe Adverse Events

Adverse Event	Associated with Dose No.	No. of Days Post Associated Dose (Duration)	Severity	Relationship to Study Treatment	If Not Related, Alternative Etiology	Action Taken with Study Treatment	Subject Discontinued Due to AE	Outcome	MedDRA System Organ Class	MedDRA Preferred Term
Subject ID: , Tr	eatment Group: ,	AE Number:							 	
Comments:										
Subject ID: , Tr	eatment Group: ,	AE Number:								
Comments:										

14.3.3 Narratives of Deaths, Other Serious and Significant Adverse Events

(not included in SAP, but this is a placeholder for the CSR)

14.3.4 Abnormal Laboratory Value Listings (by Subject)

Table 46:Listing of Abnormal Laboratory Results - Chemistry

Subject ID	Treatment Group	Sex	Age (years)	Planned Time Point	Actual Study Day	Laboratory Parameter (Units)	Result (Severity)	Relationship to Treatment	If Not Related, Alternate Etiology	Action Taken with Study Treatment	Subject Discontinued Due to Result?

	Listing				Juits IIch	natorogy					
Subject ID	Treatment Group	Sex	Age (years)	Planned Time Point	Actual Study Day	Laboratory Parameter (Units)	Result (Severity)	Relationship to Treatment	If Not Related, Alternate Etiology	Action Taken with Study Treatment	Subject Discontinued Due to Result?

 Table 47:
 Listing of Abnormal Laboratory Results - Hematology

14.3.5 Displays of Laboratory Results

14.3.5.1 Chemistry Results

Table 48: Laboratory Results by Parameter, Maximum Severity, Time Point, and Treatment Group – Any Chemistry Parameter

			No	one	Mi Gra	ild / 1de 1	Mod Gra	erate/ de 2	Sev Gra	ere/ de 3	Mis	sing
Time Point	Treatment Group	Ν	n	%	n	%	n	%	n	%	n	%
Baseline	HEV-239	х	х	xx	х	XX	х	XX	Х	XX	х	XX
	Placebo											
Day 8	HEV-239											
	Placebo											
Day 36	HEV-239											
	Placebo											
Day 187	HEV-239											
	Placebo											
Max Severity Post Baseline	HEV-239											
	Placebo											

Note: The "Max Post Baseline" rows indicate the maximum severity experienced by each subject at any time point post baseline, including unscheduled assessments. N=Number of subjects in the Safety Population

	Treatment		No	one	Mi Gra	ild/ ide 1	Mode Gra	erate/ .de 2	Sev Gra	ere/ de 3	Miss	sing
Time Point	Group	Ν	n	%	n	%	n	%	n	%	n	%
Baseline	HEV-239	х	х	XX	х	XX	Х	XX	х	XX	х	XX
	Placebo											
Day 8	HEV-239											
	Placebo											
Day 36	HEV-239											
	Placebo											
Day 187	HEV-239											
	Placebo											
Max Severity Post Baseline	HEV-239											
	Placebo											

Table 49: Laboratory Results by Parameter Time Point, and Treatment Group – Creatinine

Note: The "Max Post Baseline" rows indicate the maximum severity experienced by each subject at any time point post baseline, including unscheduled assessments. N=Number of subjects in the Safety Population

Tables with similar format:

Table 50: Laboratory Results by Parameter Time Point, and Treatment Group – ALT

	- Any Chen	listi y 1 al a						
	Treatment		M Gra	ild/ nde 1	Mod Gra	erate/ ide 2	Sev Gra	rere/ .de 3
Time Point	Group	Ν	n	%	n	%	n	%
Day 8	HEV-239	х	х	XX	X	XX	Х	XX
	Placebo							
Day 36	HEV-239							
	Placebo							
Day 187	HEV-239							
	Placebo							
Max Severity Post Baseline	HEV-239							
	Placebo							

Table 51:Abnormal Laboratory Results Related to Study Treatment by Parameter, Maximum Severity, Time Point, and Treatment Group
– Any Chemistry Parameter

Note: The "Max Post Baseline" rows indicate the maximum severity of abnormal laboratory results related to study treatment experienced by each subject at any time point post baseline, including unscheduled assessments. N=Number of subjects in the Safety Population

Table 52:Abnormal Laboratory Results Related to Study Treatment by Parameter, Maximum Severity, Time Point, and Treatment Group
- Creatinine

			M Gra	ild/ de 1	Mod Gra	erate/ de 2	Sev Gra	ere/ de 3
Time Point	Treatment Group	Ν	n	%	n	%	n	%
Day 8	HEV-239	х	х	xx	х	XX	х	XX
	Placebo							
Day 36	HEV-239							
	Placebo							
Day 187	HEV-239							
	Placebo							
Max Severity Post Baseline	HEV-239							
	Placebo							

Note: The "Max Post Baseline" rows indicate the maximum severity experienced by each subject at any time point post baseline, including unscheduled assessments. N=Number of subjects in the Safety Population

Tables with similar format:

 Table 53:
 Abnormal Laboratory Results Related to Study Treatment by Parameter, Maximum Severity, Time Point, and Treatment Group

 - ALT

Time Point	Treatment Group	Ν	Mean	Standard Deviation	Median	Min, Max
Baseline	HEV-239	х	xx.x	XX.X	XX.X	XX.X, XX.X
	Placebo					
Day 8	HEV-239					
	Placebo					
Day 8, Change from Baseline	HEV-239					
	Placebo					
Day 36	HEV-239					
	Placebo					
Day 36, Change from Baseline	HEV-239					
	Placebo					
Day 187	HEV-239					
	Placebo					
Day 187, Change from Baseline	HEV-239					
	Placebo					

Table 54: Laboratory Summary Statistics by Parameter, Time Point, and Treatment Group – Creatinine

Note: N=Number of subjects in the Safety Population

Tables with similar format:

Table 55: Laboratory Summary Statistics by Parameter, Time Point, and Treatment Group – ALT

14.3.5.2 Hematology Results

Table 56: Laboratory Results by Parameter, Maximum Severity, Time Point, and Treatment Group – Any Hematology Parameter

	Treatment		None		Mild / Grade 1		Moderate/ Grade 2		Severe/ Grade 3		Missing	
Time Point	Group	Ν	n	%	n	%	n	%	n	%	n	%
Baseline	HEV-239	Х	х	xx	х	xx	х	xx	х	xx	х	XX
	Placebo											
Day 8	HEV-239											
	Placebo											
Day 36	HEV-239											
	Placebo											
Day 187	HEV-239											
	Placebo											
Max Severity Post Baseline	HEV-239											
	Placebo											

Note: The "Max Post Baseline" rows indicate the maximum severity experienced by each subject at any time point post baseline, including unscheduled assessments.

N =Number of subjects in the Safety Population

	Treatment	ient	None		Mild/ Grade 1		Moderate/ Grade 2		Severe/ Grade 3		Missing	
Time Point	Group	Ν	n	%	n	%	n	%	n	%	n	%
Baseline	HEV-239	х	х	xx	х	xx	х	xx	х	xx	х	XX
	Placebo											
Day 8	HEV-239											
	Placebo											
Day 36	HEV-239											
	Placebo											
Day 187	HEV-239											
	Placebo											
Max Severity Post Baseline	HEV-239											
	Placebo											

Table 57: Laboratory Results by Parameter, Maximum Severity, Time Point, and Treatment Group – Hemoglobin

Note: The "Max Post Baseline" rows indicate the maximum severity experienced by each subject at any time point post baseline, including unscheduled assessments. N = Number of subjects in the Safety Population

	Treatment		No	one	Mi Gra (Lo	ild/ de 1 ow)	Mi Gra (Hi	ld/ de 1 gh)	Mode Gra (Lo	erate/ de 2 ow)	Mode Gra (Hi	erate/ de 2 gh)	Sev Gra (Lo	ere/ de 3 w)	Seve Gra (Hi	ere/ de 3 gh)	Mis	sing
Time Point	Group	Ν	n	%	n	%	n	%	n	%	n	%	n	%	n	%	n	%
Baseline	HEV-239	Х	х	XX	х	XX	х	XX	х	XX	х	XX	х	XX	х	XX	х	XX
	Placebo																	
Day 8	HEV-239																	
	Placebo																	
Day 36	HEV-239																	
	Placebo																	
Day 187	HEV-239																	
	Placebo																	
Max Severity Post Baseline	HEV-239																	
	Placebo																	

Table 58: Laboratory Results by Parameter, Maximum Severity, Time Point, and Treatment Group – WBC

Note: The "Max Post Baseline" rows indicate the maximum severity experienced by each subject at any time point post baseline, including unscheduled assessments. N = Number of subjects in the Safety Population

	Treatment	Freatment –		one	Mi Gra	ld/ de 1	Mode Gra	erate/ de 2	Sev Gra	ere/ .de 3	Mis	sing
Time Point	Group	Ν	n	%	n	%	n	%	n	%	n	%
Baseline	HEV-239	х	х	XX	х	XX	Х	XX	Х	XX	Х	XX
	Placebo											
Day 8	HEV-239											
	Placebo											
Day 36	HEV-239											
	Placebo											
Day 187	HEV-239											
	Placebo											
Max Severity Post Baseline	HEV-239											
	Placebo											

Table 59: Laboratory Results by Parameter, Maximum Severity, Time Point, and Treatment Group – Absolute Neutrophil Count

Note: The "Max Post Baseline" rows indicate the maximum severity experienced by each subject at any time point post baseline, including unscheduled assessments. N =Number of subjects in the Safety Population

Tables with similar format:

 Table 60:
 Laboratory Results by Parameter, Maximum Severity, Time Point, and Treatment Group – Absolute Eosinophil Count

 Table 61:
 Laboratory Results by Parameter, Maximum Severity, Time Point, and Treatment Group – Platelets

Table 62:Abnormal Laboratory Results Related to Study Treatment by Parameter, Maximum Severity, Time Point, and
Treatment Group – Any Hematology Parameter

	Treatment		Mi Gra	ild/ de 1	Mode Gra	erate/ de 2	Severe/ Grade 3		
Time Point	Group	Ν	n	%	n	%	n	%	
Day 8	HEV-239	х	Х	XX	Х	XX	х	XX	
	Placebo								
Day 36	HEV-239								
	Placebo								
Day 187	HEV-239								
	Placebo								
Max Severity Post Baseline	HEV-239								
	Placebo								

Note: The "Max Post Baseline" rows indicate the maximum severity of abnormal laboratory results related to study treatment experienced by each subject at any time point post baseline, including unscheduled assessments. N = Number of subjects in the Safety Population

Table 63:Abnormal Laboratory Results Related to Study Treatment by Parameter, Maximum Severity, Time Point, and Treatment Group
–Hemoglobin

	Treatment		M Gr:	ild/ nde 1	Mod Gra	erate/ de 2	Sev Gra	ere/ de 3
Time Point	Group	Ν	n	%	n	%	n	%
Day 8	HEV-239	х	х	xx	x	XX	х	xx
	Placebo							
Day 36	HEV-239							
	Placebo							
Day 187	HEV-239							
	Placebo							
Max Severity Post Baseline	HEV-239							
	Placebo							

Note: The "Max Post Baseline" rows indicate the maximum severity experienced by each subject at any time point post baseline, including unscheduled assessments. N = Number of subjects in the Safety Population

Table 64: Abnormal Laboratory Results Related to Study Treatment by Parameter, Maximum Severity, Time Point, and Treatment Group -WBC

Treatment			Mild/Grade 1 (Low)		Mild/Grade 1 (High)		Moderate/Grade 2 (Low)		Moderate/Grade (High)		Severe/Grade 3 (Low)		Severe/Grade 3 (High)	
Time Point	Group	Ν	n	%	n	%	n	%	n	%	n	%	n	%
Day 8	HEV-239	х	х	xx	х	XX	х	xx	х	xx	х	xx	х	XX
	Placebo													
Day 36	HEV-239													
	Placebo													
Day 187	HEV-239													
	Placebo													
Max Severity Post Baseline	HEV-239													
	Placebo													

Note: The "Max Post Baseline" rows indicate the maximum severity experienced by each subject at any time point post baseline, including unscheduled assessments. N = Number of subjects in the Safety Population

Table 65:Abnormal Laboratory Results Related to Study Treatment by Parameter, Maximum Severity, Time Point, and Treatment Group
-Absolute Neutrophil Count

			Mi Gra	ild/ de 1	Mod Gra	erate/ de 2	Severe/ Grade 3		
Time Point	Treatment Group	Ν	n	%	n	%	n	%	
Day 8	HEV-239	х	х	xx	х	XX	х	XX	
	Placebo								
Day 36	HEV-239								
	Placebo								
Day 187	HEV-239								
	Placebo								
Max Severity Post Baseline	HEV-239								
	Placebo								

Note: The "Max Post Baseline" rows indicate the maximum severity experienced by each subject at any time point post baseline, including unscheduled assessments. N = Number of subjects in the Safety Population

Tables with similar format:

- Table 66:Abnormal Laboratory Results Related to Study Treatment by Parameter, Maximum Severity, Time Point, and Treatment Group
– Absolute Eosinophil Count
- Table 67:Abnormal Laboratory Results Related to Study Treatment by Parameter, Maximum Severity, Time Point, and Treatment Group
–Platelets

Time Point	Treatment Group	N	Mean	Standard Deviation	Median	Min, Max
Baseline	HEV-239	х	XX.X	XX.X	XX.X	xx.x, xx.x
	Placebo					
Day 8	HEV-239					
	Placebo					
Day 8, Change from Baseline	HEV-239					
	Placebo					
Day 36	HEV-239					
	Placebo					
Day 36, Change from Baseline	HEV-239					
	Placebo					
Day 187	HEV-239					
	Placebo					
Day 187, Change from Baseline	HEV-239					
	Placebo					

Table 68:	Laboratory Summary Statistics by Parameter, Time Point, and Treatment Group –
	Hemoglobin

Note: N = Number of subjects in the Safety Population

Tables with similar format:

- Table 69:Laboratory Summary Statistics by Parameter, Time Point, and Treatment Group –
WBC
- Table 70:Laboratory Summary Statistics by Parameter, Time Point, and Treatment Group –
Absolute Neutrophil Count
- Table 71:Laboratory Summary Statistics by Parameter, Time Point, and Treatment Group –
Absolute Eosinophil Count
- Table 72:Laboratory Summary Statistics by Parameter, Time Point, and Treatment Group –
Platelets

